**Table 7: Weight-based Dosing Regimen**

Weight	Loading Dose (Day 1, Month 1, Month 2)	Maintenance Dose (Month 3 and Beyond)
<10 kg	6.0 mg/kg monthly for 3 months	3.0 mg/kg monthly
$\geq 10$ to $< 20$ kg	6.0 mg/kg monthly for 3 months	6.0 mg/kg every 3 months
$\geq 20$ kg	3.0 mg/kg monthly for 3 months	3.0 mg/kg every 3 months

For patients who weigh  $<20$  kg, the dose will be based on a weight obtained within 7 days prior to dosing. During periods of time when the COVID-19 pandemic impedes the ability of these patients to travel to the study site or healthcare professionals to go to patients' homes, a weight from up to 6 weeks prior to the planned monthly dose or up to 4 months prior to the planned quarterly dose may be used to calculate the amount of lumasiran to be administered.

For patients who weigh  $\geq 20$  kg, the dose may be based on a weight obtained up to 4 months prior to the planned quarterly dose.

Patients with weight increases crossing the threshold for the next weight-based dosing category ( $<10$  kg to  $\geq 10$  kg or  $<20$  kg to  $\geq 20$  kg) will follow the new dosing regimen for the remainder of the study or until the next dosing category threshold is reached (ie, patients will not switch back to the lower-weight dosing schedule if their body weight subsequently decreases).

Patients in maintenance dosing who transition from <10 kg to  $\geq$ 10 kg will continue to receive monthly doses at 3.0 mg/kg until the next visit that coincides with [Table 4](#), whereby they will follow every-3-months dosing as per [Table 4](#) until the end of the study.

If a patient does not receive a dose of lumasiran within the specified dosing window, the Investigator should contact the Medical Monitor. After such consultation, the dose may be administered or considered missed and not administered.

If a patient misses multiple consecutive doses, the Investigator, in consultation with the Medical Monitor, will discuss whether the patient will be able to continue the study (see Section [4.3](#)).

Patients whose disease progresses to requiring a dialysis regimen will continue on their planned dosing regimen prior to starting dialysis therapy. The lumasiran dose will be administered as soon as feasible following the end of dialysis, eg, within 2 hours of completing the dialysis session. If a patient does not receive a dose of lumasiran within the specified dosing window, the Investigator should contact the Medical Monitor. After such consultation, the dose may be administered or considered missed and not administered.

Additional details can be found in the Pharmacy Manual. In addition, instructions and procedures related to administration of lumasiran by a caregiver will be provided in the Patient/Caregiver Storage and Administration Instructions.

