**Table 1: Schedule of Assessments –Primary Analysis Period (Screening through Month 6): All Patients**

*After Month 6, patients with weight <10 kg follow Table 2. Patients with weight ≥10 kg follow Table 4.*

Study Period Study Visit	Notes	Screening	6-Month Primary Analysis Period							
			Baseline	Wk 2	M1	M2	M3	M4	M5	M6
Study Day (±Visit Window)		-60 to -1	1	15 (±3)	29 (±14)	57 (±14)	85 (±14)	113 (±14)	141 (±14)	169 (±14)
Informed consent	Section 8.1.1	X								
Demographics	Section 6.1	X								
Medical history	Changes occurring between screening and Day 1 are to be updated prior to dosing. Section 6.1	X	X							
Inclusion/exclusion criteria	Section 4.	X								
Full physical examination	Section 6.5.3	X								X
Abbreviated physical examination	Section 6.5.3		X	X	X	X	X	X	X	
Height/length	Centimeters. Section 6.5.2	X	X		X	X	X	X	X	X
Body weight	Kilograms. Section 5.2.2; Section 6.5.2	X	X		X	X	X	X	X	X
Vital signs	Predose on dosing days. On Day 1 (only), also measured 30 ± 10 minutes postdose. Section 6.5.1	X	X	X	X	X	X	X	X	X
12-lead ECG	Local 12-lead, singlicate, predose ECGs. Section 6.5.4	X	X				X			X
DNA sample for PH1/AGXT mutation analysis	Only for patients without documented PH1 genetic analysis.	X								
Exploratory DNA sample (optional)	Where allowed per local regulations. Section 6.6		X							
Clinical laboratory assessments	Serum creatinine and LFTs are repeated if not collected <30 days before Day 1 (Section 5.2.3.1); Section 6.1; Section 6.5.5	X	X	X	X	X	X	X	X	X

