**Table 1: Schedule of Assessments –Primary Analysis Period (Screening through Month 6): All Patients**

*After Month 6, patients with weight <10 kg follow Table 2. Patients with weight ≥10 kg follow Table 4.*

Study Period Study Visit	Notes	Screening	6-Month Primary Analysis Period							
			Baseline	Wk 2	M1	M2	M3	M4	M5	M6
Study Day (±Visit Window)		-60 to -1	1 (±3)	15 (±14)	29 (±14)	57 (±14)	85 (±14)	113 (±14)	141 (±14)	169 (±14)
Study drug dosing in patients <10 kg	Dosing must be at least 21 days apart. Section 5.2.2; Table 7		X		X	X	X	X	X	X
Study drug dosing in patients ≥10 kg			X		X	X	X			X
Blood samples for PK analyses	See Table 5 for blood collection timepoints.		X							X
Blood samples for PD analyses	Collected predose, when applicable. Section 6.3.	X	X		X	X	X	X	X	X
24-hour urine collections for PD analyses	At Screening and Month 6, three collections are performed predose. For patients unable to comply, a single catheterized 24-hour collection may be performed. Section 6.2	X								X
Single-void urine collections for PD analysis (3 collections)	Following screening, 3 single-void collections are collected within 7 days predose (first morning voids are preferred). Section 6.2	X			X	X	X	X	X	X
Blood sample for pyridoxine (vitamin B6) levels	Only in patients receiving therapeutic pyridoxine. Do not collect within 6 hours of pyridoxine dose. Section 5.3	X	X				X			X
Renal stone events	Renal stone events are not considered AEs or SAEs. Section 6.3.3									
Renal ultrasound	Performed as per procedure manual. Section 6.3.4	X								X
Developmental assessment	Vineland Adaptive Behavior Scale. Section 6.7	X								X
Patient/caregiver experience and impact questionnaire	Section 6.8	X								X
ADA sample	Collect predose. Section 6.5.5.1		X		X		X			X

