**Table 2: Schedule of Assessments – Long-term Extension Period (Month 7 to Month 35): Patient Weight <10 kg**

*Patients whose weight increases to  $\geq 10$  kg continue monthly dosing until the next visit that coincides with Table 4 and then patients will follow Table 4 until the end of the study. Patients with weight <10 kg follow Table 3 after Month 35.*

Study Visit		M7; M8	M9	M10; M11	M12	M13; M14	M15	M16; M17	M18	M19; M20	M21	M22; M23	M24	M25; M26	M27	M28; M29	M30	M31; M32	M33	M34; M35
Study Day (±Visit Window)	Note	197, 225 (±14)	253 (±14)	281, 309 (±14)	337 (±14)	365, 393 (±14)	421 (±14)	449, 477 (±14)	505 (±14)	533, 561 (±14)	589 (±14)	617, 645 (±14)	673 (±14)	701, 729 (±14)	757 (±14)	785, 813 (±14)	841 (±14)	869, 897 (±14)	925 (±14)	953, 981 (±14)
Full physical examination	Section 6.5.3				X				X					X			X			
Abbreviated physical examination	Section 6.5.3	X	X	X		X	X	X			X				X				X	
Height/length	Centimeters. Section 6.5.2		X		X		X		X		X		X		X		X		X	
Body weight	Kilograms. Section 5.2.2; Section 6.5.2	X	X	X	X	X	X	X	X	X	X	X	X	X	X	X	X	X	X	X
Vital signs	Section 6.5.1	X	X	X	X	X	X	X	X	X	X	X	X	X	X	X	X	X	X	X
12-lead ECG	Local 12-lead, singlicate, predose ECGs. Section 6.5.4				X									X						
Clinical laboratory assessments	Section 5.2.3.1; Section 6.5.5	X	X	X	X	X	X	X	X	LFT only										
Study drug dosing	Dosing must be at least 21 days apart. Section 5.2.2; Table 7	X	X	X	X	X	X	X	X	X	X	X	X	X	X	X	X	X	X	X
Blood samples for PK analyses	See Table 5 for blood collection timepoints.				X				X				X							
Blood samples for PD analyses	Section 6.3	X (Opt)	X	X (Opt)	X	X (Opt)	X	X (Opt)	X		X		X		X		X		X	
24-hour urine collection for PD analyses (1 collection)	Section 6.2				X				X				X				X			
Single-void urine collections (3 collections)	Collected within 7 days predose (first morning voids preferred). Section 6.2	X (Opt)	X	X (Opt)	X	X (Opt)	X	X (Opt)	X		X		X		X		X		X	

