**Table 4: Schedule of Assessments – Long-term Extension Period (Month 9 to End of Study): Patient Weight  $\geq 10$  kg**

*Patients following Table 2 or Table 3 whose weight increases to  $\geq 10$  kg continue monthly dosing until the next visit that coincides with this table. Patients will then follow this table until the end of the study.*

Study Period		Long-term Extension Period																EOT	EOS/ET	Safety Follow-up
Study Visit		M9	M12	M15	M18	M21	M24	M27	M30	M33	M36	M39	M42	M45	M48	M51	M54	M57	M60	(Pts who DC treatment)
Study Day ( $\pm$ Visit Window)	Notes	253 ( $\pm 28$ )	337 ( $\pm 28$ )	421 ( $\pm 28$ )	505 ( $\pm 28$ )	589 ( $\pm 28$ )	673 ( $\pm 28$ )	757 ( $\pm 28$ )	841 ( $\pm 28$ )	925 ( $\pm 28$ )	1009 ( $\pm 28$ )	1093 ( $\pm 28$ )	1177 ( $\pm 28$ )	1261 ( $\pm 28$ )	1345 ( $\pm 28$ )	1429 ( $\pm 28$ )	1513 ( $\pm 28$ )	1597 ( $\pm 28$ )	1681 ( $\pm 28$ )	Every 84 days ( $\pm 28$ )
Full physical examination	Section 6.5.3		X		X		X		X		X		X		X		X		X	
Abbreviated physical examination	Section 6.5.3	X		X		X													X	
Height/length	Centimeters. Section 6.5.2	X	X		X		X		X		X		X		X		X		X	
Body weight	Kilograms. Section 6.5.2	X	X	X	X	X	X	X	X	X	X	X	X	X	X	X	X	X		
Vital signs	Section 6.5.1	X	X	X	X	X	X		X		X		X		X		X		X	
12-lead ECG	Local 12-lead, singlicate, predose ECGs. Section 6.5.4		X				X				X				X				X	
Clinical laboratory assessments	Section 5.2.3.1; Section 6.5.5	X	X	X	X	X	X	LFT only	X	LFT only	X	LFT only	X	LFT only	X	LFT only	X	LFT only	X	
Pregnancy testing	Females of child-bearing potential only. Section 6.5.5.2	X	X	X	X	X	X	X	X	X	X	X	X	X	X	X	X	X		
Study drug dosing	Dosing must be at least 21 days apart. Section 5.2.2	X	X	X	X	X	X	X	X	X	X	X	X	X	X	X	X			
Blood samples for PK analyses	See Table 5 for timepoints.		X		X		X		X											
Blood samples for PD analyses	Section 6.3	X	X	X	X	X	X	X (opt)	X	X (opt)	X	X (opt)	X	X (opt)	X	X (opt)	X	X (opt)	X	

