#### **5.2.3.1. Liver Function Test Criteria for Withholding, Monitoring and Stopping Lumasiran Dosing**

1. For patients who weigh <20 kg, liver function test (LFT) results (see [Table 10](#)) are to be obtained within 7 days prior to dosing and results are to be reviewed prior to each dose of lumasiran. During periods of time when the COVID-19 pandemic impedes the ability of patients to travel to the study site or healthcare professionals to go to patients' homes and LFT assessments are not feasible within 7 days prior to the dose, LFT test results up to 6 weeks prior to the planned monthly dose or up to 4 months prior to the planned quarterly dose may be reviewed to determine whether the dose can be administered.

For patients who weigh  $\geq$ 20 kg, LFT results may be reviewed up to 4 months prior to the planned quarterly dose to determine whether the dose can be administered.

2. Consult the Laboratory Manual for the blood draw priority list based on patient weight. Central laboratory results are preferable. If not available, local laboratory results may be used; however, if a local assessment is drawn, a serum chemistry sample must also be drawn for analysis at the central laboratory.
3. For any ALT or AST elevation  $>3\times$  ULN, central laboratory results should be used to guide subsequent monitoring as detailed in [Table 8](#).

4. For any ALT or AST elevation  $>3 \times$  ULN:
  - a. If local laboratory results are obtained, confirm using central laboratory, as soon as possible, ideally within 2 to 3 days, but no later than 7 days.
  - b. If an alternative cause is found, provide appropriate care.
  - c. If an alternative cause is not found, perform assessments per [Table 8](#) and [Table 11](#).
5. For any ALT or AST elevation  $>3 \times$  ULN without alternative cause that is accompanied by clinical symptoms consistent with liver injury (eg, nausea, right upper quadrant abdominal pain, jaundice) or elevated bilirubin to  $\geq 2 \times$  ULN or international normalized ratio (INR)  $\geq 1.5$ , permanently discontinue dosing.
6. For confirmed ALT or AST elevations  $>3 \times$  ULN without alternative cause and not accompanied by symptoms or elevated bilirubin  $\geq 2 \times$  ULN or INR  $\geq 1.5$ , see [Table 8](#):

**Table 8: Monitoring and Dosing Rules for Asymptomatic Patients with Confirmed Isolated Elevations of ALT and/or AST  $>3\times$  ULN, with No Alternative Cause Identified**

Transaminase Level	Action

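### For a child who passes 10 kg between the Month 3 dose and Month 6, the protocol gives conflicting dosing schedules up to Month 9

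*Protocol*

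**What the plan says.** The relevant instructions sit in several places.

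- **Protocol Section 5.2.2, text under Table 7.** A child already in maintenance who crosses 10 kg "will continue to receive monthly doses at 3.0 mg/kg until the next visit that coincides with" Table 4, and from then on is dosed every three months.
- **Table 4 title.** The schedule is the "Long-term Extension Period (Month 9 to End of Study): Patient Weight" 10 kg or more. Its first column is Month 9 (Day 253).
- **Table 1 header.** After Month 6, patients under 10 kg go to Table 2. For the others: "Patients with weight ≥10 kg follow Table 4". The split is on weight alone.
- **Table 1 dosing rows.** The row "Study drug dosing in patients ≥10 kg" has doses at Day 1 and Months 1, 2, 3 and 6, and none at Months 4 or 5. It has no exception for a child who has just crossed. The note at the dosing rows reads "Dosing must be at least 21 days apart. Section 5.2.2; Table 7".
- **Table 2 header.** Children who reach 10 kg "continue monthly dosing until the next visit that coincides with Table 4". Table 2 has Month 7 and 8 visits with weight, laboratory tests and dosing.
- **Table 4 header.** It repeats the bridging rule, but only for children arriving from Table 2 or Table 3.
- **Synopsis and SAP 2.1.** Both give the bridging rule without naming Table 4. They refer to the assessment schedule for the heavier weight group (10 kg or more in the synopsis, 10 to under 20 kg in the SAP).

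**The concern.** A site treating a child who was under 10 kg at the Month 3 dose and is 10 kg or more at Month 6 has two instructions that cannot both be followed. Section 5.2.2 makes doses due at Months 7 and 8. The Table 1 header moves the child to a schedule with no visit in either month. The bridging notes do not close the gap: Table 2 is reserved by the Table 1 header for children under 10 kg, and the Table 4 note does not mention children coming directly from Table 1.

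At stake is which maintenance regimen a very young child receives for three months. Safety checks are also involved. Below 20 kg, liver tests "are to be obtained within 7 days prior to dosing and results are to be reviewed prior to each dose of lumasiran", and dose weight has the same 7-day limit, apart from the COVID-19 allowances. Among the extension tables, only Table 2 schedules these checks at Months 7 and 8.

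The case is foreseeable. Section 3.4 requires at least one child under 12 months and under 10 kg, and Section 1.4 puts median weight at about 10 kg at one year.

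**Working it through.** The plan states no total dose for this child, so there is no figure to reproduce. The check compares the schedules and adds nominal mg/kg doses.

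**Inputs**

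- Study days (Tables 1, 2 and 4): Month 6 = 169, Month 7 = 197, Month 8 = 225, Month 9 = 253.
- Maintenance dose (Table 7): 3.0 mg/kg monthly below 10 kg; 6.0 mg/kg every three months from 10 to under 20 kg.
- Primary window (SAP 3.1 and 7.1): Months 3 to 6, four visits.
- Urine timing (Table 1): "3 single-void collections are collected within 7 days predose".
- Planned enrollment: 20.

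**Step 1. Month 6 up to, but not including, Month 9**

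| Reading | Month 6 | Month 7 | Month 8 | Total (mg/kg) |
|---|---|---|---|---|
| Section 5.2.2 | 3.0 | 3.0 | 3.0 | 9.0 |
| Table 1 row for 10 kg or more, then Table 4 | 6.0 | 0 | 0 | 6.0 |
| Mixed: Section 5.2.2 at Month 6, then Table 1 header | 3.0 | 0 | 0 | 3.0 |

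Dose interval under Section 5.2.2: 197 − 169 = 28 days. With no Month 7 or 8 dose: 253 − 169 = 84 days.

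**Step 2. Doses at Months 3 to 5, given before the Month 6 urine**

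Section 5.2.2 gives 3 × 3.0 = 9.0 mg/kg whenever the crossing occurs. If the row for 10 kg or more is applied from the crossing onward:

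- crossing before the Month 4 dose: 3.0 + 0 + 0 = 3.0 mg/kg
- crossing before the Month 5 dose: 3.0 + 3.0 + 0 = 6.0 mg/kg
- crossing after the Month 5 dose: 3.0 + 3.0 + 3.0 = 9.0 mg/kg, no difference

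**Step 3. Months 3 to 8 combined**

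Section 5.2.2: 9.0 + 9.0 = 18.0 mg/kg. Row for 10 kg or more from the crossing onward: 3.0 + 6.0 = 9.0, 6.0 + 6.0 = 12.0, or 9.0 + 6.0 = 15.0 mg/kg, in the order of Step 2.

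**Step 4. Reach into the primary window**

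Urine is taken before the dose, so an omitted Month 4 dose can first show at Month 5 and an omitted Month 5 dose only at Month 6. At most 2 of the child's 4 visits are affected. With 20 patients that is 2 / (20 × 4) = 2 / 80 = 2.5% of patient-visits per affected child. Omitted Month 7 and 8 doses cannot affect the window.

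**The case against.** The strongest reply is that the bridging rule is stated repeatedly: in the synopsis, in Section 5.2.2, in the headers of Tables 2, 3 and 4 and in SAP 2.1. Table 1's own dosing note points to Section 5.2.2. The Table 1 header only names the next schedule and sets no dose, so the specific dosing section should govern. That is a reasonable order of precedence. It does not produce a Month 7 or 8 visit for the child, though, and a site working from Table 4 sees no dose to miss. Nothing would then prompt the call to the Medical Monitor that Section 5.2.2 asks for when a dose falls outside its window.

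A second reply is that the synopsis and SAP 2.1 wording allows Month 6 to be the switch visit, because Table 1 has a dosing row for children of 10 kg or more with a Month 6 dose. The child then gets 6.0 mg/kg at Month 6 and the next dose at Month 9, a regimen planned in Table 7. This reading is fair, and it means that following the Table 1 header need not leave the child underdosed. It still disagrees with Section 5.2.2, which names Table 4.

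A third reply is that the 7-day weight and liver-test rules bind every dose below 20 kg, whichever table is in use. That is correct. The requirement itself is intact; only the scheduled visit to carry it out is missing.

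A reader might infer that the protocol directs 3.0 mg/kg to cover 84 days, half of the 6.0 mg/kg planned for that interval. It does not. That total arises only if a site applies Section 5.2.2 at Month 6 and then disregards it at Months 7 and 8.

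**Conclusion.** The conflict is in the current text and should be corrected, but it is a minor dosing-instruction error. For a child under 10 kg at the Month 3 dose and at least 10 kg by Month 6, the two internally consistent readings give 9.0 mg/kg in three doses or 6.0 mg/kg in one dose between Month 6 and Month 9. All readings converge at Month 9.

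A reader might take this to concern every child who crosses 10 kg by Month 6. It does not: the bridging sentence covers maintenance only, and a child who crosses during loading takes the heavier group's regimen from Month 3.

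A reader might also infer a threat to the primary result. The documents do not support that. The Month 7 and 8 doses come after the window. The Month 4 and 5 doses matter only if a site applies the row for 10 kg or more against Section 5.2.2, and then for at most 2.5% of patient-visits per affected child.

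That few children are affected is an assumption. The plan requires only one child under 10 kg, and the Amendment 2 rationale reports one patient at 8.5 kg with the rest above 10 kg. That is a snapshot and does not exclude earlier crossings. The totals are nominal sums of mg/kg doses and assume no missed doses and a weight below 20 kg.

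**What to change.** 1. In the Table 1 header, and as a note on its dosing row for 10 kg or more, state that a child under 10 kg at the Month 3 dose who crosses 10 kg at or before Month 6 stays on 3.0 mg/kg monthly under Section 5.2.2. The child follows Table 2 at Months 7 and 8, including weight and liver tests, and moves to Table 4 at Month 9.
2. Extend the bridging note in the Table 4 header to children coming from Table 1.
3. Change the synopsis and SAP 2.1 to name Table 4, as Section 5.2.2 does.

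The cost is wording in four places in the protocol and one in the SAP. No new visit type is needed, because the Month 7 and 8 columns already exist in Table 2. If the sponsor intends Month 6 to be the switch visit, Section 5.2.2 should be changed to say so, and the other places aligned to that.

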### **5.2.3. Dose Modifications**

Dose modifications are not permitted.

If a study drug-related AE occurs in a patient that the Investigator judges as presenting a potential risk to the patient for further dosing, the study drug dose may be held at the discretion of the Investigator and the Medical Monitor should be contacted.

#### **5.2.3.1. Liver Function Test Criteria for Withholding, Monitoring and Stopping Lumasiran Dosing**

1. For patients who weigh <20 kg, liver function test (LFT) results (see [Table 10](#)) are to be obtained within 7 days prior to dosing and results are to be reviewed prior to each dose of lumasiran. During periods of time when the COVID-19 pandemic impedes the ability of patients to travel to the study site or healthcare professionals to go to patients' homes and LFT assessments are not feasible within 7 days prior to the dose, LFT test results up to 6 weeks prior to the planned monthly dose or up to 4 months prior to the planned quarterly dose may be reviewed to determine whether the dose can be administered.

For patients who weigh  $\geq$ 20 kg, LFT results may be reviewed up to 4 months prior to the planned quarterly dose to determine whether the dose can be administered.

2. Consult the Laboratory Manual for the blood draw priority list based on patient weight. Central laboratory results are preferable. If not available, local laboratory results may be used; however, if a local assessment is drawn, a serum chemistry sample must also be drawn for analysis at the central laboratory.
3. For any ALT or AST elevation  $>3\times$  ULN, central laboratory results should be used to guide subsequent monitoring as detailed in [Table 8](#).

4. For any ALT or AST elevation  $>3 \times$  ULN:
  - a. If local laboratory results are obtained, confirm using central laboratory, as soon as possible, ideally within 2 to 3 days, but no later than 7 days.
  - b. If an alternative cause is found, provide appropriate care.
  - c. If an alternative cause is not found, perform assessments per [Table 8](#) and [Table 11](#).
5. For any ALT or AST elevation  $>3 \times$  ULN without alternative cause that is accompanied by clinical symptoms consistent with liver injury (eg, nausea, right upper quadrant abdominal pain, jaundice) or elevated bilirubin to  $\geq 2 \times$  ULN or international normalized ratio (INR)  $\geq 1.5$ , permanently discontinue dosing.
6. For confirmed ALT or AST elevations  $>3 \times$  ULN without alternative cause and not accompanied by symptoms or elevated bilirubin  $\geq 2 \times$  ULN or INR  $\geq 1.5$ , see [Table 8](#):

**Table 8: Monitoring and Dosing Rules for Asymptomatic Patients with Confirmed Isolated Elevations of ALT and/or AST  $>3\times$  ULN, with No Alternative Cause Identified**

Transaminase Level	Action
$>3\times$ to $5\times$ ULN	

May continue dosing

Evaluate the initial elevation in LFT per the following assessments:

Table 11 (all assessments to be performed; see Section 6.5.5.4 for guidance on maximal pediatric blood volumes)

Hematology, serum chemistry, LFT per Table 10

Coagulation (prothrombin time, partial thromboplastin time, international normalized ratio)

Monitor at least every two weeks: LFT per Table 10

If elevation persists for <math>\geq 2</math> months, must discuss with the Medical Monitor before continuing dosing

$>5\times$ to $8\times$ ULN	

Hold lumasiran dosing until recovery to <math>\leq 1.5\times</math> ULN or baseline; may resume dosing after discussion with the Medical Monitor

Evaluate the initial elevation in LFT per the following assessments:

Table 11 (all assessments to be performed once)

Hematology, serum chemistry, LFT per Table 10

Coagulation (prothrombin time, partial thromboplastin time, international normalized ratio)

Monitor at least weekly: LFT per Table 10 until ALT and/or AST is declining on 2 consecutive draws, then may decrease monitoring to biweekly

If ALT or AST rises to <math>>5\times</math> ULN following resumption of dosing, permanently discontinue dosing

$>8\times$ ULN	Permanently discontinue dosing after confirmation by the central laboratory of the transaminase value

Abbreviations: ALT=alanine aminotransferase; AST=aspartate aminotransferase; LFT=liver function tests; ULN=upper limit of normal.

Notes: In addition to these criteria, other assessments or evaluations may be performed per Investigator discretion, as appropriate.

